Burden and risks

N/A (no intervention involved)

Recruitment and consent

Informed consent has been waived based on the unreasonable effort due to the large size and its observational nature.

1. Introduction and rationale

The impact of donor and recipient sex combination on kidney transplant outcomes has been studied extensively, but with inconclusive results. From an immunologic perspective, the transplantation of male donor kidneys into female recipients was associated with an increased risk of graft failure and mortality due to H-Y minor histocompatibility antigens.^{1,2} Another theory, based on nephron overload and hyperfiltration, suggests that male recipients of female donor kidneys tend to experience worse outcomes due to the smaller size of female kidneys.³ Additionally, the influence of sex hormones has also been explored. Aufhauser et al.⁴ found that estrogen acts as a protective factor against ischemia-reperfusion injury (IRI), resulting in a significantly lower incidence of delayed graft function (DGF) in female recipients compared to male recipients. However, recent research by Vinson et al.⁵ demonstrates that female recipients have higher excess mortality rates and graft loss rates than males. These findings seem conflicting, and primarily focus on deceased donor kidney transplantation.

In terms of living donor kidney transplantation (LDKT), Kayler et al.⁶ analyzed a transplant database encompassing 30,258 LDKTs between 1990 and 1999. Their study revealed a significant advantage in graft survival for male recipients of male donor kidneys compared to the other combinations. Another study involving 5,716 HLA-identical sibling kidney transplantations between 1985 and 2000 demonstrated that female recipients tend to have better graft survival rates regardless of the donor's sex.³ Despite advancements in clinical practice, no such large-scale studies exploring this question have been conducted in the subsequent two decades.

2. Objective(s)

- I. To investigate the impact of different donor and recipient sex combinations on the graft survival following living donor kidney transplantation
- II. To investigate the impact of different donor and recipient sex combinations on the graft function (eGFR) following living donor kidney transplantation

3. Study type

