4.5. Sample size calculation

To acquire enough data to make the research results robust, the estimated subject number is ~2000 patients.

5. Methods

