5.1. Research methods

Retrospective data from our transplant database were used to identify patients undergoing LDKT between January 2010 and December 2020. LDKTs were categorized into male-to-male, female-to-male, male-to-female, and female-to-female groups based on donor-recipient sex combinations. The primary outcome was death-censored graft survival. The secondary outcomes included patient survival, delayed graft function (DGF), acute rejection and graft function.

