7.2 Secondary study parameters/endpoints

The secondary outcomes included patient survival, delayed graft function (DGF), acute rejection and graft function. Graft function is defined by estimated glomerular filtration rate (eGFR) using the Chronic Kidney Disease Epidemiology Collaboration (CKD-EPI) equation.

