7.4 Analysis

Continuous variables were reported as medians with interquartile ranges (IQRs), and categorical variables were reported as frequencies with percentages. The Kruskal-Wallis test was used to compare continuous variables, and the chi-squared test was used to compare categorical variables. Kaplan-Meier curves and the log-rank test were used to compare patient and graft survival rates. Cox-regression was performed to identify the risk factors for death-censored graft failure. Variables with a p-value < 0.1 in the univariate analysis were included in the multivariate analysis. The proportional hazards assumption was evaluated through Schoenfeld residuals. A two-sided p-value < 0.05 was considered statistically significant. All statistical analyses were conducted using R version 4.2.2.

8. Ethical considerations

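### The only adjusted model selects its variables by univariate p<0.1 and does not say that the sex combination stays in, so Objective I can end without an adjusted estimate or with true confounders left out

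*Combined protocol and SAP*

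**What the plan says.** Objective I (section 2) is "To investigate the impact of different donor and recipient sex combinations on the graft survival following living donor kidney transplantation". Section 5.1 defines the exposure: "LDKTs were categorized into male-to-male, female-to-male, male-to-female, and female-to-female groups based on donor-recipient sex combinations". The primary outcome (section 7.1) is death-censored graft survival.

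Section 7.4 offers two routes to an answer:

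- **Unadjusted:** "Kaplan-Meier curves and the log-rank test were used to compare patient and graft survival rates". No stratification or adjustment is mentioned.
- **Multivariable:** "Cox-regression was performed to identify the risk factors for death-censored graft failure", with the entry rule "Variables with a p-value < 0.1 in the univariate analysis were included in the multivariate analysis".

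The other tests named in 7.4 (Kruskal-Wallis, chi-squared) are also unadjusted. The nearest thing to a covariate list is section 7.3. It gives broad categories (age, gender, history, operative details, follow-up information) and names no donor variable. No section says that the sex combination is retained in the multivariable model, or which confounders that model must contain.

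**The concern.** The rule is built for finding risk factors, whereas the objective is to estimate the effect of one named exposure. Three problems follow.

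1. **The exposure can drop out.** Read literally, a sex combination with a crude p-value of 0.1 or more does not enter the multivariable model. Only the log-rank test and the univariate Cox result then remain.
2. **Confounders are chosen on the wrong criterion.** A crude p-value against the outcome reflects strength of association and event count. It does not show whether a variable distorts the comparison between sex groups, so a true confounder can be discarded. This holds even if the screen was meant for covariates only.
3. **Post-transplant variables are not excluded.** This is a conditional and lesser point. Section 7.2 states: "The secondary outcomes included patient survival, delayed graft function (DGF), acute rejection and graft function". The plan does not propose these as covariates, but the rule would admit them if they were screened. Section 1 links recipient sex to DGF ("a significantly lower incidence of delayed graft function (DGF) in female recipients compared to male recipients"), so DGF could lie on the causal pathway.

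The groups were not randomised, so the adjusted estimate is what makes Objective I interpretable. An effect hidden by confounding is the one most likely to fail a crude screen, and it is also the one that most needs adjustment.

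**Working it through.** **The plan's own figure.** Section 4.5 says "To acquire enough data to make the research results robust, the estimated subject number is ~2000 patients". No event rate, effect size or power accompanies it, so it can be neither reproduced nor refuted. The argument does not depend on it.

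**Assumptions (not in the documents).** D = 150 or 250 graft failures; four groups, one of which differs by hazard ratio HR and holds a share p of patients.

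**Step 1: chance that the exposure fails the screen.** The exposure has 3 degrees of freedom, so the critical value at 0.1 is 6.251. The test statistic is approximately noncentral chi-square with

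ncp = D × p × (1 − p) × (ln HR)².

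For p = 0.25 and HR 1.5, (ln 1.5)² = 0.1644:

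- D = 150: 150 × 0.1875 × 0.1644 = 4.62, chance of failing 46.2%
- D = 250: 250 × 0.1875 × 0.1644 = 7.71, chance of failing 25.3%

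| Share of differing group | HR | Fails, D = 150 | Fails, D = 250 |
|---|---|---|---|
| 25% | 1.3 | 71.1% | 58.6% |
| 25% | 1.5 | 46.2% | 25.3% |
| 25% | 1.75 | 20.0% | 4.9% |
| 25% | 2.0 | 6.5% | 0.6% |
| 15% | 1.5 | 59% | 41% |
| 15% | 2.0 | 18% | 4% |
| 35% | 1.5 | 39% | 18% |
| 35% | 2.0 | 3% | 0.1% |

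Weighting by share of events instead of share of patients lowers the equal-group figures: 39.5% and 18.6% at HR 1.5, 2.4% and 0.1% at HR 2.0.

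**Step 2: chance that a true confounder is screened out.** For a binary covariate with 40% prevalence, z = ln(HR) × √(D × 0.4 × 0.6), tested two-sided at 0.1. At HR 1.25 and D = 150, z = 0.223 × √36 = 1.34.

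If the covariate has prevalence 30% in one group and 60% in the other, omitting it shifts the exposure HR by about (1 + 0.6(HR − 1)) / (1 + 0.3(HR − 1)). At HR 1.25 this is 1.15 / 1.075 = 1.07.

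| Confounder HR | Dropped, D = 150 | Dropped, D = 250 | Shift if omitted |
|---|---|---|---|
| 1.25 | 61.9% | 46.6% | 1.07 |
| 1.5 | 21.5% | 6.7% | 1.13 |
| 2.0 | 0.6% | 0.0% | 1.23 |

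**Step 3: masking.** Simulation of 400 cohorts of 2000 per scenario, with exponential times, uniform 4 to 14 year censoring and about 230 to 260 events. The true exposure HR is 1.5. A covariate with HR 1.42 per SD is set lower in the affected group. Monte Carlo standard error is about 2.5 points.

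| Covariate shift | Crude HR | Exposure dropped | Power via screen | Power, both forced in |
|---|---|---|---|---|
| none | 1.48 | 25% | 67% | 67% |
| 0.25 SD lower | 1.35 | 47% | 53% | 64% |
| 0.5 SD lower | 1.26 | 65% | 35% | 59% |

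With a weaker covariate (HR 1.2 per SD, 0.5 SD lower) the exposure is dropped in 43%, with power 55% against 62%. With a true HR of 2.0 (covariate HR 1.42, 0.5 SD lower) it is dropped in 6%, with power 94% against 98.5%.

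A second simulation used a binary confounder (HR 1.5, prevalence 30% in the affected group and 60% elsewhere, about 244 events). The exposure was dropped in 52% of cohorts, the confounder in 25%, and at least one of them in 67%. The mean exposure HR was 1.49 with both forced in and 1.32 without the confounder, against a true value of 1.5.

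**The case against.** **The sex combination is the study's organising variable, so the authors surely meant to keep it.** That is a reasonable reading, but the text does not say so. If it is right, the fix only records the intent. It also leaves the second problem untouched, because confounders are still picked by crude p-value.

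**The unadjusted comparisons remain.** True. What can be lost is the adjusted estimate, and the point claims no more than that.

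**The illustration leans one way.** This stands in part. If two equal groups differ, as with a pure recipient-sex effect, ncp at HR 1.5 is 150 × 0.25 × 0.1644 = 6.17 or 250 × 0.25 × 0.1644 = 10.28. The chance of failing is then 35% to 14%, not 46% to 25%. Confounding in the opposite direction inflates the crude effect: the exposure is then dropped in only 4% to 10% of simulated cohorts, with no loss of power. The documents do not show which direction applies.

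**The confounders most often dropped are weak.** This also stands. Each brings a modest bias, a factor of 1.07 to 1.13 for hazard ratios of 1.25 to 1.5. Selection by p-value is also common practice, though common use does not make a crude p-value a measure of confounding.

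**The post-transplant point is speculative.** It is conditional. Section 1 itself says the findings it reviews come mainly from deceased-donor transplantation, whereas this study is living-donor only. It justifies one clarifying sentence in the plan and carries little weight otherwise, although section 7.3 does list follow-up information without limit.

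**Section 7.4 is in the past tense, so the analysis may already be done.** If so, a prespecified list is no longer possible in the strict sense. The model can still be refitted and reported as a change from plan.

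**Conclusion.** The concern holds and should be fixed before the results are relied on. It rests on the text: there is one multivariable model, entry is by univariate p<0.1, the exposure is not protected, and no covariate set is fixed. Followed as written, the plan can leave its primary objective without an adjusted estimate, or with one whose confounders were decided by crude p-values.

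The size depends on assumed event counts, group shares, hazard ratios and covariate shifts, none of which the documents supply. Under those assumptions the risk of losing the exposure is material up to a hazard ratio of about 1.5. It is small at 2.0 unless the differing group is small, and largest where confounding masks the effect. Bias from any single dropped confounder is likely to be modest.

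**What to change.** Replace the screening sentence in section 7.4 with wording such as:

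> The Cox model for death-censored graft failure includes the four-level sex combination whatever its p-value, together with a prespecified set of pre-transplant donor and recipient covariates chosen on subject-matter grounds (for example recipient age, donor age, donor-recipient relationship, HLA mismatch, transplant year and centre). No variable is selected by univariate p-value. DGF, acute rejection and post-transplant eGFR are not covariates in this model.

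The sponsor should set the exact list before analysis and size it, in degrees of freedom, to the observed number of graft failures; the exposure alone uses 3. The plan should also say whether sex enters as one four-level factor or as donor sex, recipient sex and their interaction. If a risk-factor search is still wanted, keep the p<0.1 screen only in a separate model labelled exploratory.

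The cost is a wording change through the amendment route in section 12, possibly extraction of some further database fields, and slightly wider confidence intervals (not quantified here). Where the effect is large or unconfounded, the gain in power is small or nil, but an adjusted estimate is always reported.

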7.1 Main study parameters/endpoints

The primary outcome was death-censored graft survival.

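### Section 7.4 applies one unadjusted 5% threshold to five outcomes, names no deciding test for the primary outcome and gives the secondary tests no status; the chance of a false-positive sex-combination result is about 15-26%, not 5%.

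*Combined protocol and SAP*

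**What the plan says.** Section 7.1 names a single primary outcome: "The primary outcome was death-censored graft survival". Section 7.2 adds four more: "The secondary outcomes included patient survival, delayed graft function (DGF), acute rejection and graft function". Section 2 lists two objectives without ranking them. Objective I concerns graft survival. Objective II is "To investigate the impact of different donor and recipient sex combinations on the graft function (eGFR) following living donor kidney transplantation", so an outcome that section 7.2 calls secondary is also a stated objective.

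Section 5.1 defines the exposure: "LDKTs were categorized into male-to-male, female-to-male, male-to-female, and female-to-female groups based on donor-recipient sex combinations". That makes four groups, so an overall comparison has 3 degrees of freedom.

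Section 7.4 gives two analyses that bear on the primary outcome. The first is unadjusted: "Kaplan-Meier curves and the log-rank test were used to compare patient and graft survival rates". The second is a model: "Cox-regression was performed to identify the risk factors for death-censored graft failure". Variables enter the multivariable version if their univariate p-value is below 0.1, and sex combination is not exempted from that screen. For the remaining outcomes, section 7.4 offers Kruskal-Wallis for continuous and chi-squared for categorical variables. The only criterion for a positive finding is "A two-sided p-value < 0.05 was considered statistically significant". No section gives a hierarchy, an adjustment, a deciding test for the primary outcome or a statement that secondary results are exploratory.

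**The concern.** Two gaps combine. First, the plan does not say which analysis answers Objective I. A log-rank comparison of four sex combinations ignores differences between the groups in age and other risk factors. The Cox model can adjust for them, but it is described as looking for risk factors, not as estimating the effect of the exposure. Read literally, the screen could remove sex combination, and there would then be no adjusted estimate of the effect the study is about. If the two analyses disagree, nothing says which one prevails.

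Second, the status of the four secondary tests is open. A single p<0.05 for eGFR, patient survival, delayed graft function or acute rejection could be presented as an effect of sex combination, on the same footing as the primary result. The introduction describes earlier findings as inconclusive and apparently conflicting. A study with several unranked routes to significance is poorly placed to settle them.

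**Working it through.** **Inputs from the document.** Threshold 0.05, two-sided (7.4); one primary outcome (7.1) and four secondary outcomes (7.2); four groups (5.1); two analyses relevant to the primary outcome and a 0.1 screening threshold (7.4). I read 7.4 as planning one overall 3-df test per outcome. The plan states no family-wise error rate, power or event count, so there is no derived figure of its own to reproduce.

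**Assumptions.** Sex combination has no effect on any outcome. Correlations between tests are not in the documents and are varied below.

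**Step 1: independent tests.** The chance of at least one p<0.05 in k tests is 1 - 0.95^k.
- Five outcomes: 1 - 0.95^5 = 22.6%.
- Five outcomes plus a second primary analysis: 1 - 0.95^6 = 26.5%. This is an upper figure, because log-rank and Cox use the same events.

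**Step 2: correlated tests.** Each overall test was simulated as a 3-df chi-squared statistic, with a common correlation between outcomes for the underlying normal components. In the six-test column, the Cox components correlate with the log-rank components at 0.95 (lower figure) or 0.8 (higher figure).

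| Correlation between outcomes | Five tests | Six tests |
|---|---|---|
| 0 | 22.7% | 24.0-25.1% |
| 0.3 | about 21% | 22.4-23.4% |
| 0.5 | 18.8% | 19.9-21.1% |
| 0.7 | about 15.5% | 16.4-17.7% |

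Steps 1 and 2 together span about 15% to 26%.

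**Step 3: primary outcome alone.** If either analysis may count, the false-positive rate is about 6.6% at a log-rank/Cox correlation of 0.95, 8.0% at 0.8 and 8.5% at 0.7. If the adjusted test is run only when the univariate result is below 0.1, it is about 6% over the same correlations. The range is therefore about 6-8.5%.

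**Step 4: contrasts the text does not plan (hypothetical).** With four equal groups:
- All six pairs at 5% each: 20.3% for one outcome (studentized range); 1 - (1 - 0.203)^5 = about 68% for five independent outcomes.
- Three contrasts against a reference group: 12.6% for one outcome; 1 - (1 - 0.126)^5 = about 49% for five.

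**Step 5: what 'likely' would need.** Passing one half takes ln(0.5)/ln(0.95) = 13.5, so 14 independent tests. The planned overall tests number five or six.

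**The case against.** The plan already has a ranking of a kind: section 7.1 names one primary outcome and section 7.2 labels the rest, eGFR included, as secondary. That stands, and it limits the inflation for the primary outcome to the choice between log-rank and Cox, which is small. The two objectives add no tests either, since graft survival and eGFR are already among the five outcomes. The label does not, however, say which analysis decides the primary outcome or what a significant secondary result may be used to claim.

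A reader might infer that a chance finding is likely, and support this with the 68% in step 4. The documents do not bear that out. Section 7.4 mentions no pairwise comparison, and on the tests it does name, the chance stays well under one half. Contrasts are still foreseeable, because the hypotheses in the introduction concern particular combinations and a four-level factor in a Cox model ordinarily yields three contrasts against a reference. The figures in step 4 show what would follow if they were tested without a rule, not what the plan contains.

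A reader might also infer that every p-value in the study counts towards a sex-combination claim. It does not: the 0.1 threshold serves variable selection, and a chance covariate finding in the Cox model is not an effect of sex combination.

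Finally, formal error control over secondary outcomes is partly convention in a retrospective cohort without intervention. I accept that. It argues against requiring a full gated procedure, but not against naming the deciding test and stating the status of the others.

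**Conclusion.** The concern holds in a limited form. The plan names one primary outcome but not its deciding test, allows the exposure to drop out of the adjusted model, and leaves the standing of four secondary tests unstated at an uncorrected 5%. With no true effect, the chance of at least one false-positive sex-combination result over the planned overall tests is about 15-26%, roughly three to five times the nominal level. For the primary outcome alone it is about 6-8.5% if either analysis may count. These figures assume one overall 3-df test per outcome, correlations of 0 to 0.7 between outcomes and, short of full independence, 0.7 to 0.95 between the two primary analyses. They measure chance only. Confounding of the unadjusted log-rank comparison is a further reason not to let it decide.

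**What to change.** In section 7.4:
1. Name the 3-df test of sex combination in the adjusted Cox model for death-censored graft failure, at two-sided 5%, as the single deciding test for Objective I.
2. State that the sex-combination term stays in that model regardless of the p<0.1 screen.
3. Describe the log-rank test as supportive.
4. Report patient survival, delayed graft function, acute rejection and eGFR as estimates with 95% confidence intervals, labelled secondary or exploratory. Say explicitly that this covers Objective II.
5. Label any pairwise contrasts exploratory unless they are adjusted for multiplicity.

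**Cost.** The change is wording only and needs no new data. The overall primary test keeps its full 5%. What is given up is that a significant secondary result or an unadjusted log-rank result can no longer be claimed on its own as a confirmed effect.

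If the investigators choose to adjust all six pairs, those comparisons lose power. How much depends on the number of graft failures, which the documents do not give, so the event counts below are assumptions. For one pair out of four equal groups, the pair holds d = D/2 of the D failures. The hazard ratio detectable with 80% power is exp(z × 2/√d), with z = 2.802 at 5% and 3.480 at 5%/6.

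| Assumed failures D | d | At 5% | At 5%/6 |
|---|---|---|---|
| 240 | 120 | 1.67 | 1.89 |
| 120 | 60 | 2.06 | 2.46 |
| 60 | 30 | 2.78 | 3.56 |

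Any detectable-effect figure added to the plan should likewise be marked as an assumption and given as a range.

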8.1 Regulation statement

The study will be conducted according to the principles of the Declaration of Helsinki (64th World Medical Association General Assembly, Fortaleza, Brazil, October 2013). The following guidelines also apply to this study;

- Gedragscode Gezondheidszorgonderzoek 2022.
- Privacy regulation of participating hospitals
- EU General Data Protection Regulation and the Dutch Act on Implementation of the General Data Protection Regulation (in Dutch: Uitvoeringswet 'Algemene Verordening Gegevensbescherming' (UAVG)).

This study has been exempted by the Medical Research Ethics Committee (MREC); in Dutch: Non-WMO Review Committee (NWTC). Following review of the protocol, the MREC concluded this study is not subject to the Medical Research Involving Human Subjects Act (WMO). They concluded that the study is a medical/ scientific research, but no patients are subjected to procedures or are required to follow rules of behavior.

8.2 **Informed consent**

Will the subjects be asked for informed consent?

- Yes (*Upload Participant Information Letter and Informed Consent*)
- No, consent already given in previous study (*Upload Participant Information Letter and Informed Consent previous study*)
- No, this research will be performed under the exception consent (*Upload form Care for data Template, in Dutch: Formulier uitzondering toestemming*)
- Other (e.g. partly, indirectly) *Please describe the situation.*

8.3 **Recruitment and informed consent procedures**

Not applicable, patients will not be asked to consent to their data being used for the current study.

8.4 **Exception consent**

All cases in the transplant database have already provided informed consent for their data to be shared with the Dutch Transplant foundation for future research. The informed consent is asked before a recipient is placed on the transplant waiting list.

9. **Handling and storage of data / images / sound recordings / photos / film recordings**

9.1 **Data / images / sound recordings / photos / film recordings**

Patient clinical data, including demographics, surgical information and follow-up information, will be used. These data are obtained for regular healthcare purposes.

9.2 **Privacy protection**

To ensure the subject's privacy is protected, each patient will be assigned a unique code that does not include any personal identifiers such as patient ID or date of birth. This code will be used throughout the study to identify the data associated with each subject. A designated data manager (the principal investigator), is responsible for the assignment of unique codes and ensure that the coding process is consistently applied. The key table linking the unique codes to the personal identifiers will be stored in a secure file that is separate from the research data. Only authorized personnel, such as the principal investigator, will have access to this database. The handling of personal data has to comply with the EU General Data Protection Regulation and the Dutch Act on Implementation of the General Data Protection Regulation (in Dutch: Algemene Verordening Gegevensbescherming en Uitvoeringswet Algemene Verordening Gegevensbescherming).

9.3 **Handling and storage of data**

Research data will be stored in the format of SPSS in Erasmus MC departmental X drive with limited access to the PI and co-investigators, and will be handled confidentially. Only authorized personnel can view research data that can be traced to individual participants. These persons are the members of the research team, members of the health care inspection, and members of

the Medical Research Ethics Committee of the participating hospital. Data review may be necessary in order to ensure the reliability and quality of the research. The handling of personal data is in compliance with the GDPR General Data Protection Regulation (in Dutch AVG 25-05-2018) and the privacy regulation of the Erasmus MC. In line with Erasmus MC guidelines, data will be kept 10 years after it is collected.

9.4 Handling and storage of images / sound recordings / photos / film recordings

Not applicable, this study does not involve images, sound recordings, photos, or film recordings

9.5 Approval of access to data / images / sound recordings / photos / film recordings

For each study site, access to data has been approved by the department head or board of directors, as applicable.

10. Handling and storage of human material

